2.2. Endpoints

Primary Efficacy Endpoint

- Parasitological response (PCR corrected) at Day 28 post first dose of study medication.

Secondary Efficacy Endpoints

- Parasitological responses (PCR corrected) at Days 7, 14, 21, 35, and 42 post first dose of study medication;
- Parasitological responses (PCR uncorrected) at Days 7, 14, 21, 28, 35, and 42 post first dose of study medication;
- Parasite counts at each visit– number of asexual *P. falciparum* parasites per microliter of blood.

Pharmacokinetic Evaluation

- Pharmacokinetic exposure of AZCQ.

Safety Endpoints

- Safety and tolerability endpoints including spontaneously reported adverse events, temperature, hemoglobin concentrations, and the EIU assessment.

3. STUDY DESIGN

This is an open label, single arm non-comparative out-patient study in pregnant women during their second and third trimesters of pregnancy. Women will be screened for peripheral parasitaemia. Women who are screened but not included in the study (screen failures) will be referred to their doctors and will be given standard antenatal care (ANC) including IPTp. Subjects with asymptomatic parasitemia (counts of 80 -100,000/ μ L) will receive a single 3-day course of AZCQ IPTp regimen. Subjects will be followed up on a weekly basis up to Day 42 after the first dose, and following delivery or at termination of pregnancy for EIU safety assessments. After completing Day 42 evaluation, all subjects will continue to receive standard antenatal care including IPTp with SP if the gestational age allows additional IPTp course(s). The parasitological response will be evaluated on Days 7, 14, 21, 28, 35 and 42. Pharmacokinetics evaluation will be conducted on blood samples collected from the subjects who consented for such test. Systemic concentrations of AZ, CQ and desethyl-CQ will be evaluated on Day 0 predose, Day 2 predose, 2 hours (as close to 2 hours as possible) and 8 hours (window: 4 to 12 hours) post dose, and at a random time point on Days 7 and 14. In addition, due to the long half-life of CQ, systemic concentrations of CQ and desethyl-CQ will also be measured at a random time point on Days 21 and 28. All subjects will also be followed up for EIU safety assessments following delivery or termination of pregnancy. The insecticide treated bed-nets will be given to all subjects on Day 0 of the study with installation verified during Day 1 home visit by fieldworker(s).

4. SUBJECT SELECTION

This study can fulfill its objectives only if appropriate subjects are enrolled. The following eligibility criteria are designed to select subjects for whom protocol treatment is considered appropriate. All relevant medical and non-medical conditions should be taken into consideration when deciding whether this protocol is suitable for a particular subject. Subjects who fail to meet the selection criteria for the study will be referred to appropriate physician for receiving standard ANC care including IPTp treatment as per national/local antenatal care guidelines.

4.1. Inclusion Criteria

Subject eligibility should be reviewed and documented by an appropriately qualified member of the investigator's study team before that subject is included in the study.

Subjects must meet all of the following inclusion criteria on Day 0 to be eligible for enrollment into the study:

1. Primigravidae and secundigravidae pregnant women at ≥ 14 and ≤ 30 weeks of gestational age (confirmed by ultrasound examination).
2. Evidence of asymptomatic parasitemia with *Plasmodium falciparum* mono-infection (confirmed by microscopy) with parasite counts in the range of 80-100,000/ μ L on thick blood smears.

3. Evidence of a personally signed and dated informed consent document indicating that the subject (or a legally acceptable representative if a subject is <18 years of age) has been informed of all pertinent aspects of the study and that all questions by the subject have been sufficiently answered. Assent will be obtained from subjects <18 years of age.
4. Subjects who are willing and able to comply with scheduled visits, treatment plan, laboratory tests, and other study procedures.
5. Subjects who agree to be supervised for treatment administration, and are available for all follow up visits as per protocol.

4.2. Exclusion Criteria

Subjects presenting with any of the following will not be randomized in the study:

1. Age <16 years old or >35 years old.
2. Multiple gestations (more than one fetus) as per the ultrasound results at screening.
3. Clinical symptoms of malaria.
4. Hemoglobin <8 g/dL (measured at baseline).
5. Any condition requiring hospitalization or evidence of severe concomitant infection at time of presentation.
6. Use of antimalarial drugs in previous 4 weeks.
7. History of convulsions, hypertension, diabetes or any other chronic illness that may adversely affect fetal growth and viability.
8. Inability to tolerate oral treatment in tablet form.
9. Known allergy to the study drugs (AZ, CQ, and SP) or to any macrolides or sulphonamides.
10. Present history of smoking or alcohol or drug abuse since becoming pregnant.
11. Participation in other studies within 30 days before the current study begins and/or during study participation.
12. Inability to comprehend and/or unwillingness to follow the study protocol.
13. Concurrent participation in another investigational study.
14. Previously randomized in this study.

15. Requirement to use medication during the study that might interfere with the evaluation of the study drug of AZ or CQ or is contra-indicated during pregnancy per package inserts.
16. Severe acute or chronic medical or psychiatric condition or laboratory abnormality that may increase the risk associated with study participation or investigational product administration or may interfere with the interpretation of study results and, in the judgment of the investigator, would make the subject inappropriate for entry into this study. Examples would include but not limited to:
 - a. Symptomatic HIV infection, including physical findings that suggest immunocompromised status (eg, oral candidiasis);
 - b. Neurological conditions which may predispose to complications during pregnancy, including seizure disorders;
 - c. Severe psychosis or major disorder that may interfere with the conduct of the study or adherence to study medication;
 - d. Known, clinically significant pre-existing renal or hepatic disease.
17. Evidence of current obstetric complications that may adversely impact the pregnancy and/or fetal outcomes, including presence of congenital anomalies, placenta previa or abruption.
18. Known severe sickle cell (SS) disease or sickle-hemoglobin C (SC) anemia.
19. Known family history of prolonged QT syndrome, serious ventricular arrhythmia, or sudden cardiac death.

4.3. Randomization Criteria

Since this is a non-comparative single arm study, there is no randomization. The subjects who meet all inclusion/exclusion criteria will receive study medication at the Day 0 visit. Subjects will be assigned patient identification numbers (PID numbers) sequentially at the Day 0 visit. This unique PID number will be retained throughout the study and must appear on all CRF pages, source documents and lab data.

Study drug will be administered as open label treatment under supervision.

4.4. Life Style Guidelines

Subjects will be encouraged to stay within the area during the study period and deliver in a hospital setting. Subjects will be encouraged to use LLINs. Subjects will be followed up for EIU safety assessments following delivery or termination of pregnancy. After completing Day 42 evaluation, all subjects will continue to receive standard antenatal care including IPTp with SP if the gestational age allows additional IPTp course(s).

5. STUDY TREATMENTS

Study drug AZCQ is a fixed dose combination tablet of AZ and CQ containing 250 mg AZ and 155 mg CQ base. The dosing regimen to be evaluated in this study will consist of four AZCQ tablets (a total of 1000 mg AZ/620 mg CQ base), given orally once daily for 3 days (Days 0, 1, 2). The first dose on Day 0 and the third dose on Day 2 will be administered under supervision at the antenatal care facility (ANC), and the second dose on Day 1 will be administered at home by under supervision of a field worker.

Contraindications

The site investigator and study staff must be thoroughly aware of all contraindications and other information contained in the Package Inserts for AZ (Zithromax) and CQ (Arelen), and IB for the study medication AZCQ.

5.1. Allocation to Treatment

The investigator's knowledge of the treatment should not influence the decision to enroll a particular subject. Subjects who meet all the inclusion/exclusion criteria will be allocated to the treatment of AZCQ on Day 0.

5.2. Breaking the Blind

The study is open label.

5.3. Drug Supplies

All trial medication (AZCQ) will be supplied by Pfizer. AZCQ will be supplied as a combination tablet containing 250 mg AZ and 155 mg CQ base.

5.3.1. Formulation and Packaging

AZCQ fixed-dose combination tablets will be supplied in unit dose bottles which contain 4 tablets each and are non-patient specific.

5.3.2. Preparation and Dispensing

Only qualified personnel who are familiar with procedures that minimize undue exposure to them and to the environment should undertake the preparation, handling, and safe disposal of chemotherapeutic agents.

AZCQ will be administered to a subject under supervision by the investigator or the fieldworker once daily for three days of therapy.

5.3.3. Administration

Study medication will be administered as open label treatment under supervision. Study medication will be dispensed by the investigator or the fieldworker (Section 5.3.2). AZCQ should not be administered on an empty stomach. Each dose should be administered with a glass of water. First and third doses will be administered under supervision by investigator during ANC visits. The second dose will be administered at home under the supervision of fieldworker(s).

Any dose that is vomited within 30 minutes of administration will be repeated. If vomiting re-occurs after re-dosing on Day 0, Day 1 and Day 2, the subject will not receive further study treatments and will be provided standard treatment for malaria in pregnancy. The standard ANC care including IPTp will be given to the subject per local ANC guideline. If this happens during the home visit on Day 1, subject will be asked to return to the study physician within next 24 hours and will receive standard treatment for malaria in pregnancy. The subject will be followed through Day 42 and for pregnancy outcomes after delivery or termination of pregnancy for EIU safety assessments.

5.3.4. Compliance

The medication will be administered to the subject under supervision by investigators during ANC visit or at home under supervision by the fieldworkers.

5.4. Drug Storage and Drug Accountability

The investigator, or an approved representative (eg, pharmacist), will ensure that all study drug is stored in a secured area, under recommended storage conditions and in accordance with applicable regulatory requirements. Prior to dispensing, all study medications should be stored under the conditions per label instructions. The investigator or the fieldworker will be responsible for recording the receipt and usage of all drugs supplied and for ensuring the supervision (via the hospital pharmacist or fieldworkers where relevant) of the storage and allocation of these supplies. To ensure adequate records, all study drugs will be accounted for in the case report form and drug accountability inventory forms as instructed by Pfizer.

The investigator or the fieldworker must maintain adequate records documenting the receipt, use, loss, or other disposition of the investigational products. Pfizer will supply drug accountability forms that must be used. The forms must identify the investigational products, including batch or code numbers, and account for its disposition on a subject-by-subject basis, including specific dates and quantities. The forms must be signed by the individual who dispensed the drug, and copies must be provided to Pfizer.

At the end of the trial, Pfizer will provide instructions as to disposition of any unused investigational products. If Pfizer authorizes destruction at the trial site, the investigator must ensure that the materials are destroyed in compliance with applicable environmental regulations, institutional policy, and any special instructions provided by Pfizer. Destruction must be adequately documented.

090177e1811d3ccb\Approved\Approved On: 19-Feb-2010 20:59

5.5. Concomitant Medication(s)

The medications, not contra-indicated during pregnancy and not contra-indicated for co-administration with AZ or CQ, may be used through Day 42 following the first dose of AZCQ. After Day 42, the medications not contra-indicated during pregnancy may be used. All medications used by the subject at study entry or at any time through last study visit following the delivery or the termination of pregnancy must be recorded in the case report form. At each study visit, all medications taken since the last evaluation will be recorded.

While interactions with digoxin, ergot alkaloids, triazolam, carbamazepine, cyclosporine, hexobarbital and phenytoin have not been reported in clinical trials with AZ, they have been observed with macrolide products. Careful monitoring of subjects taking these medications is advised.

A single oral dose of AZ co-administered with nelfinavir at steady-state resulted in increased AZ serum concentrations. Although it is not necessary to adjust the dose of AZ when administered in combination with nelfinavir, close monitoring for known side effects of AZ (eg, liver enzyme abnormalities, hearing impairment) is warranted.

There have been reports which may indicate an increase in incidence and severity of adverse reactions when CQ is used with Fansidar as compared to the use of Fansidar alone (refer to Fansidar package insert).

Please refer to package inserts for AZ and CQ, and IB for AZCQ for further information regarding potential interactions between study drugs and other treatment agents

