1.4.2. Clinical Summary of Chloroquine

1.4.2.1. Clinical Pharmacology of Chloroquine

The pharmacokinetics of CQ was recently evaluated in healthy subjects in studies A0661118 and A0661186. Following oral administration, CQ is rapidly and almost completely absorbed from the gastrointestinal tract with mean peak plasma concentration ~5-7 hours. The mean plasma half-life of CQ is ~200 hours. CQ undergoes appreciable degradation in the body and the main primary active metabolite, desethyl-CQ, has a mean elimination half-life around 240 hours (10 days). Available CQ PK data suggests that there is no significant difference in the pharmacokinetics of CQ between pregnant and non-pregnant women and no dosage adjustment is required for CQ in pregnant women. Lee and colleagues⁶⁵ compared the pharmacokinetics of CQ and desethyl-CQ following administration of a standard 3 day 25 mg/kg dosing regimen of CQ in 12 pregnant and 13 non-pregnant patients with acute *P. vivax* malaria on the northwestern border of Thailand.⁶⁵ While the total area under the blood concentration-time curve ($AUC_{0-\infty}$) of CQ tended to decrease with the gestational age, the overall pharmacokinetics of CQ was not significantly different between pregnant and non-pregnant women. The AUC values for desethyl-CQ were not significantly affected by pregnancy either. The authors concluded that no dosage adjustment is required in pregnant women.⁶⁵

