6.2. Subject Withdrawal

Subjects may withdraw from the study at any time at their own request, or they may be withdrawn at any time at the discretion of the investigator or sponsor for safety, behavioral, or administrative reasons. If a subject does not return for a scheduled visit, every effort should be made to contact the subject. In any circumstance, every effort should be made to document subject outcome and pregnancy outcome, if possible. The investigator should inquire about the reason for withdrawal, request the subject to return all unused investigational product(s), request the subject to return for a final visit, if applicable, and follow-up with the subject regarding any unresolved adverse events.

If the subject withdraws from the study and also withdraws consent for disclosure of future information, no further evaluations should be performed and no additional data should be collected. The sponsor may retain and continue to use any data collected before such withdrawal of consent.

Unless a subject withdraws the consent or leaves the town/village, she should continue in the study for follow up visits through Day 42, and following delivery or termination of pregnancy for EIU safety assessment. Subject may be withdrawn from the study treatment (during the first three days) due to safety concerns (eg, adverse events, significant laboratory abnormalities, and contraindications of concomitant medications), but not from the clinical study per se unless the subject withdraws consent. The standard antenatal care including IPTp will be given to the subject per local ANC guideline. The circumstances and data surrounding these events should be clearly documented in the case report form. The

investigator must determine the primary reason for discontinuation. A discontinuation must be reported immediately to the Pfizer medical monitor or his/her designated representative if it is due to a serious adverse event (SAE).

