7.2. Safety Assessments

Safety and tolerability will be assessed by spontaneously reported adverse events, history of concomitant treatments, temperature, hemoglobin concentrations, and EIU safety assessment according to Schedule of Activities.

- Spontaneous adverse events reporting: through Day 42. Refer to Section 8 (Adverse Event Reporting) for details;
- History of concomitant treatment assessment;
- Oral temperature through Day 42;
- Hemoglobin levels: with HemoCue™, via finger stick or peripheral blood collection) at baseline and on Day 42.
- EIU Assessments:

Every attempt should be made to follow up the subject after the delivery for EIU assessment. In case of no associated serious adverse events (SAE), subjects should be followed up by fieldworkers at clinic or at home within 14 calendar days after expected date of delivery or termination of pregnancy.

- Maternal information and delivery: any history of complications during pregnancy, at and after delivery, eg, pre-eclampsia, hemorrhage, infection, etc.
- Neonatal information:
 - Outcome of pregnancy:
 - Full term live birth;
 - Premature live birth;
 - Still birth;
 - Spontaneous abortion/miscarriage;
 - Induced or elective abortion;
 - Gestational age at birth.
 - Outcome of infant:
 - Normal neonate;
 - Congenital malformation/anomaly;
 - Other neonatal problem/abnormality: include dysmaturity, neonatal illness, hospitalization, drug therapies.

Infant details: include sex, weight at birth, length at birth, head circumference at birth, APGAR scores (1/5 minutes).

- Fetal information will be collected in the event of pregnancy termination.
- Additional information and further follow-up on the neonate will be conducted when feasible and relevant to the assessment of the case if applicable.

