9.3. Safety Analysis

Adverse events, history of concomitant treatments, hemoglobin, temperature, and the EIU safety assessment will be recorded for each subject during the study according to the schedule of assessments. Standard safety reporting tables will summarize and list the safety data.

Each adverse event will be counted once according to the date of onset. If the adverse event onset was prior to the first dose of study drug and the event does not increase in severity after initiation of study drug, the adverse event is then considered to be a pre-treatment adverse event and will not be counted in the treatment-emergent adverse event incidence tables. If the onset is prior to the first dose of study drug and the severity increases thereafter, the event is counted as a treatment-emergent adverse event. An adverse event with onset after the first dose of study drug will be counted as a treatment-emergent adverse event. This rule is consistent with the treatment-emergent signs and symptoms (TESS) convention for counting adverse events.

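### Section 9.3 counts AEs after the first AZCQ dose with no end date, so events after SP or another antimalarial are pooled in the AZCQ incidence, while the protocol's sections disagree on AE collection after Day 42

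*Protocol*

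**What the plan says.** **The caution.** Section 5.5 states: "There have been reports which may indicate an increase in incidence and severity of adverse reactions when CQ is used with Fansidar". I read Fansidar as a brand of SP; the protocol does not spell this out. No interval is given. The same section has all medication recorded up to the visit after delivery or termination.

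**Planned SP.** Section 3, repeated in 4.4: "After completing Day 42 evaluation, all subjects will continue to receive standard antenatal care including IPTp with SP if the gestational age allows".

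**Possible earlier antimalarials.** After repeat vomiting, Section 5.3.3 provides standard malaria treatment and adds: "The standard ANC care including IPTp will be given to the subject per local ANC guideline". For women withdrawn from study treatment, Section 6.2 says: "The standard antenatal care including IPTp will be given to the subject per local ANC guideline". Neither sentence names SP or gives a date. Sections 6.1.2 to 6.1.5 provide for antimalarial treatment of women who develop malaria symptoms before Day 42.

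**AE collection.** Section 7.2: "Spontaneous adverse events reporting: through Day 42". Section 8.2 instead has serious and non-serious AEs recorded to the subject's last visit, and SAEs reported until one month after delivery or termination if that is later than Day 42.

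**AE counting.** Section 9.3: "An adverse event with onset after the first dose of study drug will be counted as a treatment-emergent adverse event". It gives no closing date and makes no distinction by later antimalarial use.

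**The concern.** The study has one arm, so its AE incidence will be read as the tolerability of AZCQ. Section 8.9 stresses that the combination is new to pregnant women, so clean attribution matters. After Day 42 most of the remaining pregnancy may be spent under SP-based IPTp, and the protocol itself names a possible reaction between CQ and that drug. With no comparator, events pooled across the two periods cannot be separated by contrast.

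The efficacy analysis in Section 9.2.1 already recognises the problem. It censors women who receive a concomitant antimalarial for reinfection or in the absence of parasitaemia. The safety analysis has no corresponding rule.

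The pooled period is also one in which sites hold conflicting instructions on whether to collect non-serious AEs.

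**Working it through.** The protocol states no figure on this point to reproduce. The check sets the sections side by side and then sizes the period and the overlap.

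**1. When does AE collection end?**

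| Place | What it gives |
|---|---|
| Schedule of Activities | AE assessment from Day 0 to Day 42; none in the delivery column |
| Section 7.2 | AE reporting to Day 42 |
| Section 6.1.6 (visit after delivery) | No general AE item; asks for concomitant treatment, maternal complications and neonatal outcome, and for SAEs to be reported |
| Section 8.9 | Pregnancy-related AEs to Day 42, plus pregnancy outcomes |
| Section 8.2 | All AEs to the last visit; SAEs to one month after delivery or termination |

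For non-serious AEs, Sections 7.2 and 8.2 cannot both hold. A site working from the Schedule would not ask about them at the delivery visit. A site working from Section 8.2 would record them.

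**2. What does Section 9.3 do with them?** Its only condition for a new event is onset after the first dose. Under Section 8.2, any recorded AE after SP counts. Under Section 7.2, non-serious AEs after Day 42 drop out, but SAEs up to one month after delivery still count. On either reading, an AE before Day 42 that follows another antimalarial also counts.

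**3. How long is the period?** Entry is at 14 to 30 weeks (Section 4.1).

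- Gestation at Day 42: 14 + 6 = 20 weeks to 30 + 6 = 36 weeks.
- Weeks left, assuming term at 40 weeks: 40 − 20 = 20 down to 40 − 36 = 4.
- Share of the time from first dose to term that lies after Day 42: 20/26 = 77% for entry at 14 weeks; 4/10 = 40% for entry at 30 weeks.

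Section 1.2 places SP courses before the last month of pregnancy. Women entering near 30 weeks are therefore borderline for SP at Day 42, and those entering earlier remain eligible. No distribution of gestational age is given, so the number who would receive SP cannot be derived.

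**4. How much drug remains?** Inputs from Section 1.4.2.1: half-life about 200 h for CQ and about 240 h for desethyl-CQ. Fraction remaining = 0.5^(hours since the Day 2 dose ÷ half-life), assuming mono-exponential decline and all three doses taken.

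| Day | Hours since Day 2 dose | CQ | Desethyl-CQ |
|---|---|---|---|
| 7 | 120 | 0.5^0.60 = 66% | 0.5^0.50 = 71% |
| 14 | 288 | 0.5^1.44 = 37% | 0.5^1.20 = 44% |
| 28 | 624 | 0.5^3.12 = 11.5% | 0.5^2.60 = 16.5% |
| 42 | 960 | 0.5^4.80 = 3.6% | 0.5^4.00 = 6.25% |

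Overlap is small when SP is given as planned. It could be large only if a woman received SP within the first weeks. The percentages are relative to the level after a third dose. Women who stopped early took fewer doses, so their absolute levels would be lower.

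**The case against.** A reader might infer that the reaction named in Section 5.5 will be missed, or charged to AZCQ alone. The documents do not support that, and the case against it is strong.

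- Section 8.2 still calls for all AEs to the last visit and SAEs to one month after delivery. What ends at Day 42 is scheduled assessment.
- Treatment-emergent counting is a timing convention, not attribution. Section 8.8 requires a causality judgement for every AE, and Section 8.12.1 requires SAE reports to give concomitant medication as a possible cause.
- Medication is recorded to the post-delivery visit, so SP dates will be available.
- Where scheduled assessment stops, little drug remains. Where overlap could be large, in women who stop AZCQ early, scheduled assessment continues to Day 42. That early IPTp would be SP is plausible but not stated, and neither its date nor the number of such women is given.
- Section 5.5 is a hedged caution, not a prohibition. Planned SP falls after the Day 42 window that the same section sets for avoiding drugs contra-indicated with AZ or CQ.
- Table layout is commonly left to the analysis plan, to which Section 9 refers and which is not shown.

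All of this stands except that the last item does not dispose of the point. The protocol itself fixes the counting rule, and as written the rule is open-ended. Nor can an analysis plan restore non-serious AEs that sites did not ask about. Causality judgements and medication listings help with individual events, but they do not change the incidence count.

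**Conclusion.** The point holds in limited form. Section 9.3 as written pools AEs after SP or another antimalarial into the single-arm AZCQ incidence. Capture of non-serious AEs after Day 42 will be uneven because the protocol contradicts itself on when collection ends. The affected period is 4 to 20 weeks of pregnancy per woman, assuming term at 40 weeks, against six weeks of scheduled assessment.

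The number of AEs involved cannot be estimated: the protocol gives no expected AE rate, no distribution of gestational age and no expected number of early stoppers. With about 4% of CQ and 6% of desethyl-CQ left at Day 42, the issue is mainly one of clear attribution and consistent collection. It is not evidence of a substantial unobserved interaction.

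Pregnancy outcomes need the same care in reading, since many may follow AZCQ and then SP. Nothing in Section 9.3 says they will be presented as the effect of AZCQ alone.

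**What to change.** 1. Reconcile Section 7.2, Section 8.9, the visit list in 6.1.6 and the Schedule of Activities with Section 8.2, so that one end date applies to non-serious AEs, and carry that date into Section 9.3. If collection runs to the last visit, the post-delivery visit needs an AE item. New tables alone cannot recover events that were not sought.
2. In Section 9.3, make the AZCQ table the treatment-emergent AEs and SAEs with onset before the first dose of SP or another antimalarial. Put those with later onset in a separate table, with the women who received such a drug as its denominator. Use the dates already recorded in the concomitant treatment history. Later events are kept and shown, since some may still be due to AZCQ.
3. Show the number of SP courses received beside the EIU outcomes.
4. Reconcile the Section 5.5 caution with the IPTp provisions in Sections 3, 4.4, 5.3.3 and 6.2. No clinical rule or timing is proposed here.

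The cost is one paragraph in Section 9.3, consistency edits elsewhere, possibly one added item at the final visit, and two more descriptive tables. The downside is small: the later-onset table has no comparator and can only describe.
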